3.2.2. Physical Characteristics

Physical characteristics will be presented in listing for each subject.

3.2.3. Disease Characteristics

The baseline disease assessment (AML and MDS/CMML), prior FLT3 inhibitor exposure, prior cancer therapy, medical history findings, and major protocol deviations will be presented in listings for each subject.

3.2.4. Concomitant Medications

Prior and concomitant medications will be listed.

3.3. Analysis of Efficacy

3.3.1. Primary Endpoints

No primary endpoints analysis will be provided.

3.3.2. Secondary Endpoints

No secondary endpoints analysis will be provided.

3.3.3. Exploratory/Other Analyses

Pharmacokinetic and pharmacodynamic analyses will be provided by an outside laboratory.

3.4. Analysis of Safety and Tolerability

3.4.1. Study Drug Administration

The study drug exposure will be summarized by dose cohort. The study drug administration will be presented in listing for each subject.

3.4.2. Adverse Events

All AEs will be coded based on the Medical Dictionary for Regulatory Affairs (MedDRA; Version 17.0 or higher). An AE will be considered a treatment emergent adverse event (TEAE) if the onset is after the first dose of study drug or if the condition was present at baseline but worsened after the first dose. All other AEs will be considered preexisting events.

All AEs for each subject will be listed, including Treatment Emergent status, intensity grading, relationship to study drug, action taken and outcome. Subject listings of deaths, serious TEAEs, and TEAEs leading to treatment discontinuation will be presented.

TEAE summaries will be produced for each dose cohort for subjects in FAS population. All TEAE summaries will show the number and percentage of subjects experiencing at least 1 TEAE for each preferred term, arranged by system organ class, and the number of unique occurrences of the event. Separate summaries will be produced by relationship to study medication and by severity. Subjects with multiple events will be counted only once per SOC

and preferred term. For each level of summarization, the event with the highest level of severity, grade, or strongest drug relationship will be presented. TEAEs with Grade 3 or Grade 4 and drug-related TEAEs with Grade 3 or Grade 4 will be summarized. TEAEs leading to study drug interruption or discontinuation, and Serious TEAEs will be provided in separate listings.

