1.1. Project Design

(Protocol Amendment #6). This is a Phase 1/2a, dose-escalation study of E6201, a dual MEK1 and FLT3 inhibitor, in subjects with advanced hematologic malignancies with documented FLT3 and/or Ras mutations. The Phase 1 portion of the study will be conducted as a safety run-in in up to 30 subjects to establish a recommended Phase 2 dose (RP2D). The Phase 2a portion of the study will evaluate three specific patient groups: Cohort 1 will enroll up to 26 patients with relapsed or refractory AML and confirmed FLT3 mutation (with or without a Ras mutation) without prior exposure to a FLT3 inhibitor, Cohort 2 will enroll up to 26 patients with relapsed or refractory AML and confirmed FLT3 mutation (with or without a Ras mutation) with prior exposure to a FLT3 inhibitor, and Cohort 3 will enroll up to 10 patients with relapsed or refractory AML with a confirmed Ras mutation and no FLT3 mutation. Cohorts 1 and 2 of the expansion phase will incorporate a Simon 2-stage optimal design. A total of up to N= 92 subjects will be enrolled in the study.

The accrual phase for the Phase 1 Safety Run-in portion is expected to be 24 – 27 months. The expected accrual for the Phase 2a Expansion portion is expected to be 12 months, for a total accrual period of 36 – 39 months. With the last subject followed for up to 6 months, a total study duration of 42 – 45 months is anticipated. The anticipated accrual rate for the Phase 2a portion is 4 – 6 subjects per month across all sites.

During the study, a Safety Review Committee (SRC), consisting of the actively recruiting investigators, the Medical Monitor and Boston Strategics will review data from each cohort on an ongoing basis.

Subjects who demonstrate clinical benefit (objective response or stable disease) will be allowed to continue therapy with E6201 until progression of disease, observation of unacceptable adverse events, intercurrent illness or changes in the patient's condition that prevents further study participation. Subjects will be instructed to contact their study doctor for ophthalmic evaluation should they experience disturbances in their vision.

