1.3.2. Selection and Timing of Doses

Phase 1 (Safety Run-In):

In the first cohort, the dose of E6201 will be 240 mg/m², administered as an intravenous (IV) infusion over 2 hours once weekly (Dose Level 1), on Days 1, 8, 15 and 22 of a 28-day schedule (=1 cycle). A minimum of 3 subjects will be treated. If 1 of 3 subjects experiences DLT during Cycle 1, the cohort will be expanded to 6. If ≥ 2 of 6 subjects experiences DLT by Day 28, no dose escalation to Dose Level 2 will occur. However, if 0 of 3 or ≤ 1 of 6 subjects treated at Dose Level 1 experience DLT by Day 28, dose escalation will proceed to the next cohort, 320 mg/m² weekly (Dose Level 2), administered by IV infusion over 2 hours on Days 1, 8, 15 and 22 of a 28-day schedule. A minimum of 3 subjects will be treated at this dose level. If 1 of 3 subjects treated at Dose Level 2 experiences DLT during Cycle 1, the cohort will be expanded to 6 subjects. If ≥ 2 of 6 subjects experience DLT by Day 28, no further dose escalation will occur.

However, if 0 of 3 or ≤ 1 of 6 subjects treated at Dose Level 2 experience DLT by Day 28, dose escalation will proceed to the next dose cohort, 160 mg/m² administered as an IV infusion over 2 hours twice weekly (Dose Level 3), on Days 1, 4, 8, 11, 15, 18, 22 and 25 of a 28-day schedule (=1 cycle). A minimum of 3 subjects will be treated at this dose level. If 1 of 3 subjects treated at Dose Level 3 experiences DLT during Cycle 1, the cohort will be expanded to 6 subjects. If ≥ 2 of 6 subjects experience DLT by Day 28, no further dose escalation will occur.

However, if 0 of 3 or ≤ 1 of 6 subjects treated at Dose Level 3 experiences DLT by Day 28, dose escalation will proceed to the next dose cohort, 240 mg/m² administered as an IV infusion over 2 hours twice weekly (Dose Level 4), on Days 1, 4, 8, 11, 15, 18, 22 and 25 of a 28-day schedule. A minimum of 3 subjects will be treated at this dose level. If 1 of 3 subjects treated at Dose Level 4 experiences DLT during Cycle 1, the cohort will be expanded to 6 subjects. If ≥ 2 of 6 subjects experience DLT by Day 28, no further dose escalation will occur.

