However, if 0 of 3 or ≤ 1 of 6 subjects treated at Dose Level 4 experiences DLT by Day 28, dose escalation will proceed to the next dose cohort, 320 mg/m² administered as an IV infusion over 2 hours twice weekly (Dose Level 5), on Days 1, 4, 8, 11, 15, 18, 22 and 25 of a 28-day schedule. A minimum of 3 subjects will be treated at this dose level. If 1 of 3 subjects treated at Dose Level 5 experiences DLT during Cycle 1, the cohort will be expanded to 6 subjects. If there are ≤ 1 of 6 subjects with DLT at Dose Level 5, this dose (320 mg/m² twice weekly) will be declared the MTD and RP2D. If, however, ≥ 2 of 6 subjects experiences DLT, then either 320 mg/m² weekly (Dose Level 2) or 240 mg/m² twice weekly (Dose Level 4) will be declared the MTD and RP2D based on additional factors (e.g., PK and PD parameters).

Dose-limiting toxicity will be defined as any one of the following events: prolonged myelosuppression (as defined by the National Cancer Institute [NCI] criteria specific for leukemia, i.e., marrow cellularity $< 5\%$ at ≥ 6 weeks from start of therapy without evidence of leukemia); \geq Grade 3 non-hematologic toxicity (excluding Grade 3 nausea, vomiting or diarrhea that is adequately controlled with supportive care and resolves to \leq Grade 2 within 48 hours, or Grade 3 electrolyte disturbances responsive to correction within 24 hours); \geq

Grade 3 liver function tests (LFTs) lasting > 7 days; treatment interruption > 14 days due to toxicity; or other important medical event.

Phase 2a (Expansion):

Subjects will be enrolled into the Phase 2 Expansion portion in three cohorts. Subjects will receive E6201 weekly or bi-weekly on a 28-day schedule, with the schedule and dose level established in the safety run-in portion of the study.

As of July 17, 2017, this study was terminated due to lack of sufficient efficacy in the Phase 1 dose escalation portion of the study. Therefore, the SAP will include patient listing data and dose cohort summary tables for the 28 patients enrolled in the study.

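### By-cohort TEAE tables use crude percentages over treatment periods of unequal length, with no common-window table, so reading across dose cohorts can mix dose with time on drug

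*SAP*

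**What the plan says.** Section 3.4.2 sets the layout: "TEAE summaries will be produced for each dose cohort for subjects in FAS population". It sets the statistic too: "All TEAE summaries will show the number and percentage of subjects experiencing at least 1 TEAE for each preferred term". The number of unique occurrences is shown alongside, and each subject is counted at the worst severity or grade. An event is treatment-emergent "if the onset is after the first dose of study drug or if the condition was present at baseline but worsened after the first dose"; no closing date or common cut-off is given.

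Time on drug is open-ended. Under section 1.1, subjects with a response or stable disease "will be allowed to continue therapy with E6201 until progression of disease, observation of unacceptable adverse events, intercurrent illness" or another change in condition prevents participation. Section 2.2 puts anyone given any fraction of a dose in the FAS. Section 1.4.4 has subjects replaced if they receive under 75% of their Cycle 1 drug, or miss the Day 28 evaluation, for reasons other than DLT. If dosed, they still count in the FAS. Under section 1.4.1 a subject whose dose changes keeps the same cohort number.

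On exposure, section 3.4.1 says: "The study drug exposure will be summarized by dose cohort". The seven adverse event tables in 4.1.3.2 include none limited to Cycle 1 and none using exposure. Section 4.1 lists no DLT table and section 4.3 no DLT listing.

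**The concern.** A crude percentage of subjects with at least one event rises with observation time, and so does the worst grade reached. If two dose cohorts were treated for different lengths of time, their columns will tend to differ even when toxicity per cycle is the same. Conversely, a real difference between doses can be hidden if the more toxic dose is given for less time. Event counts have the same weakness, because no person-time denominator accompanies them.

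Safety and tolerability is the Phase 1 primary objective (1.2.1), and section 3.3 plans no analysis of the efficacy endpoints. These tables are therefore a large part of what will be tabulated by dose for the 28 enrolled subjects. At stake is how a reader interprets the dose columns in the final report.

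**Working it through.** The SAP gives no figure on this point, so there is none to reproduce. The hazards, risks, durations and exposure distributions below are assumptions used to show how the tables behave.

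**1. Duration alone, no dose effect.** With constant hazard h per 28-day cycle and c cycles of exposure, P(at least one event) = 1 − exp(−h·c).
- h = 0.30: 1 − exp(−0.30) = 0.259 at 1 cycle; 1 − exp(−0.90) = 0.593 at 3 cycles.
- h = 0.15: 1 − exp(−0.15) = 0.139; 1 − exp(−0.45) = 0.362.

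The gap is 33 and 22 percentage points. In a cohort of 6 that is 6 × 0.33 = 2.0 and 6 × 0.22 = 1.3 subjects.

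**2. A real dose effect hidden.** Let the lower dose have a per-cycle risk of 20% and be given for 4 cycles, and the higher dose have twice the hazard and be given for 2.
- Whole period, lower dose: 1 − 0.8⁴ = 0.59. Higher dose: 1 − (0.8²)² = 0.59. No difference appears.
- Cycle 1 only: 0.20 against 1 − 0.8² = 0.36. The difference appears.

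**3. Is unequal exposure plausible?** Section 2.1 plans 3 to 6 subjects in each of 5 cohorts. A simulation split 28 subjects 6/6/6/5/5 (an assumption; the SAP does not give the split) and gave every cohort the same gamma exposure distribution.

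| Gamma shape | Median ratio, longest to shortest cohort mean | P(ratio > 1.5) |
|---|---|---|
| 1 (exponential) | 2.7 | 96% |
| 2 | 2.0 | 88% |
| 4 | 1.6 | 66% |

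Under these assumptions, cohorts this small would usually differ in mean exposure by chance alone, before any effect of dose on duration.

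**4. Which exposure-based rate would help?** Use step 1 with no dose effect, so a sound rate should agree at 1 and 3 cycles.
- Subjects with an event ÷ total subject-cycles: 0.259/1 = 0.26 against 0.593/3 = 0.20 (h = 0.30); 0.139/1 = 0.14 against 0.362/3 = 0.12 (h = 0.15). The distortion reverses and the longer-treated cohort looks safer.
- First events ÷ exposure censored at the first event: expected time at risk is (1 − exp(−h·c))/h. For h = 0.30 that is 0.259/0.30 = 0.864 and 0.593/0.30 = 1.978 cycles. The rates are 0.259/0.864 = 0.30 and 0.593/1.978 = 0.30, which agree.
- All events ÷ total subject-cycles also has a matching numerator and denominator.

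**5. Precision.** For 2 of 6 subjects the exact 95% confidence interval is 4% to 78%.

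**The case against.** The case for leaving the plan alone has real weight.

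- **Role of the tables.** A reader might infer that they are the evidence for choosing the dose. The SAP does not say so. Escalation follows DLTs in an early window, for example "If 1 of 3 subjects experiences DLT during Cycle 1, the cohort will be expanded to 6". Where a choice between dose levels remains, section 1.3.2 points to factors such as PK and PD. The SAP also records that "this study was terminated due to lack of sufficient efficacy in the Phase 1 dose escalation portion of the study", and it names no dose decision that these tables will feed. This stands and limits the consequence to reporting.
- **Descriptive only.** Sections 2.4.2 and 2.4.3 plan no tests or models, and no cross-dose contrast is named. This is true, but side-by-side dose columns invite comparison whether or not a test is attached.
- **Existing safeguards.** Event counts, the exposure summary and the subject listings let a reader notice an imbalance, and 4.1.3.2's companion section 4.1.3.3 tabulates laboratory results by visit. None of these gives the number of subjects with a TEAE by Day 28 without rebuilding it from listings.
- **Assumed size.** This stands in full. A reader might also infer that later cohorts had shorter exposure because the study was terminated. No section says that ongoing subjects were taken off drug at that point.
- **Day 28 is not a perfect window.** Subjects who leave early stay in the FAS, so follow-up within Cycle 1 is not wholly equal. Nor does the window match the full DLT definition, which includes a marrow criterion at 6 weeks or later. Both points stand and shape the fix.
- **Convention.** Crude incidence with a separate exposure table is a common layout for a small 3+3 study, and nothing in 3.4.2 is false. The proposal keeps that layout and adds to it.

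**Conclusion.** The point holds as a weakness built into the tables, not as a demonstrated bias. Section 3.4.2 fixes crude subject percentages and event counts over open-ended periods that differ by subject, and the separate exposure table does not adjust them. Reading across cohorts can therefore mix dose with time on drug. If the protocol closes adverse event collection at a set time after the last dose, the period would still vary with time on treatment.

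The size and direction are unknown because the SAP gives no exposure by cohort. The 26% against 59% illustration rests on a constant hazard of 0.30 per cycle, no dose effect, and 1 against 3 cycles. The stronger conclusion, that dose selection is compromised or that a toxicity gradient has been concealed, is not supported. With about 3 to 6 subjects per cohort the practical weight is modest. The change is still worth making, because it is cheap and removes most of the duration effect from the cross-dose reading.

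**What to change.** In 3.4.2 and 4.1.3.2:

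- Add a by-dose-cohort table of TEAEs with onset on Days 1 to 28, by SOC, preferred term and worst grade. Name it as the table for descriptive reading across doses.
- State in that table how many subjects per cohort were followed to Day 28.
- Keep the whole-period tables and print total subject-cycles of exposure under each column.
- If a rate is shown, use either events per total subject-cycle or first events with exposure censored at the first event. Do not divide subjects with an event by total subject-cycles.
- Do not describe the Day 1 to 28 window as matching the full DLT definition.

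The cost is a few lines of SAP text and one or two tables programmed from data already collected; no clinical rule changes. The new table does not show late-onset toxicity, which stays in the whole-period tables, and its percentages will be imprecise at these cohort sizes.

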Safety will be assessed through the monitoring of adverse events (AEs), clinical laboratory parameters (hematology and serum chemistry), vital sign measurements, ECGs and physical examinations. Adverse events will be classified according to the Medical Dictionary for Regulatory Affairs (MedDRA) and graded according to the National Cancer Institute Common Terminology Criteria for Adverse Events (NCI CTCAE) version 4.03.

Efficacy assessment for AML will be performed using a modification of the recommendations of the International Working Group (IWG) for Diagnosis, Standardization of Response Criteria, Treatment Outcomes, and Reporting Standards for Therapeutic Trials in Acute Myeloid Leukemia. Efficacy assessments for subjects with MDS or CMML will be performed using a modification of the IWG Response Criteria in Myelodysplasia.

Pharmacokinetic determinations of E6201 in plasma will be made. Levels of pERK, pFLT3, pAKT, FLT3 ITD allelic burden, FLT3 ligand and plasma inhibitory assay (PIA) for FLT3, will be measured in blood and/or bone marrow samples collected from each subject. Additional markers or mutation analysis will be undertaken, if needed. Details of the PK analysis will be outlined in a separate Pharmacokinetic Report Analysis Plan.

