4.1. Mock Tables

The following tables will be presented by dose cohort.

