4.1.3.2. Adverse Events Summaries

- Summary of Treatment Emergent Adverse Events
- Treatment Emergent Adverse Events by System Organ Class and Preferred Term
- Treatment Emergent Adverse Events by Severity
- Treatment Emergent Adverse Events by Relationship to Study Drug
- Grade 3 and Grade 4 Treatment Emergent Adverse Events by Relationship to Study Drug
- Serious Treatment Emergent Adverse Events
- Serious Treatment Emergent Adverse Events Related to Study Drug

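### The severe-TEAE summaries stop at Grade 4, so no by-cohort table is specified to give the drug-related Grade 5 or Grade 3-5 count

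*SAP*

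**What the plan says.** Section 1.1 of the SAP states that adverse events are "graded according to the National Cancer Institute Common Terminology Criteria for Adverse Events (NCI CTCAE) version 4.03".

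Section 3.4.2 sets the range of the severe-event summaries: "TEAEs with Grade 3 or Grade 4 and drug-related TEAEs with Grade 3 or Grade 4 will be summarized". The table list in section 4.1.3.2 matches it with "Grade 3 and Grade 4 Treatment Emergent Adverse Events by Relationship to Study Drug".

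Section 3.4.2 also gives a counting rule: "For each level of summarization, the event with the highest level of severity, grade, or strongest drug relationship will be presented". It does not say whether this rule is applied before or after events are restricted to Grades 3 and 4.

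Section 4.1 fixes the layout: "The following tables will be presented by dose cohort". Besides the Grade 3/4 table, section 4.1.3.2 plans "Treatment Emergent Adverse Events by Severity", "Serious Treatment Emergent Adverse Events Related to Study Drug" and four others. At subject level, section 3.4.2 promises this: "All AEs for each subject will be listed, including Treatment Emergent status, intensity grading, relationship to study drug, action taken and outcome". Deaths are to be listed. Grade 5 is not mentioned anywhere in the SAP.

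**The concern.** A severe-toxicity summary normally runs from a threshold upwards. This one has a ceiling one step below the top of the grading scale, and the ceiling appears in both the text and the table title. A programmer following the SAP would therefore build it in.

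It matters more here than in most reports. Sections 3.3.1 and 3.3.2 state that no primary or secondary efficacy endpoint will be analysed, so the by-cohort tables that remain are mainly safety tables. Safety and tolerability is part of the Phase 1 primary objective (section 1.2.1). The one table that shows severity and drug relationship together, by dose cohort, leaves out the most severe grade. If such events occurred, the table shows less severe toxicity than a Grade 3-or-higher table would.

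The stakes should not be overstated. This is an incomplete table definition, not a concealment of deaths.

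**Working it through.** The SAP gives no figure to reproduce on this point. The check sets the planned outputs side by side and then sizes the possible shift.

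**Step 1: the seven AE tables in section 4.1.3.2.** Is any specified to give a drug-related Grade 5 or Grade 3-5 count by cohort?

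| Planned table | Split by grade or severity? | Split by relationship? | Gives the count? |
|---|---|---|---|
| Overall TEAE summary | content not stated | content not stated | not specified |
| By organ class and preferred term | no | no | no |
| By severity | yes, no upper limit | no | no |
| By relationship | no | yes | no |
| Grade 3 and 4 by relationship | yes, stops at 4 | yes | no |
| Serious | no | no | no |
| Serious and related | no | related only | no |

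None of the seven is specified to give it. Only one crosses grade with relationship, and that is the capped one.

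**Step 2: the counting rule.** Suppose a subject has a Grade 4 event that becomes Grade 5 under the same preferred term.

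- If the Grade 3/4 filter is applied first, the Grade 4 record stays and the subject counts in that row.
- If the highest-grade rule is applied first, the subject's event for that term is Grade 5, the filter removes it, and the subject drops out of the row.

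The SAP does not fix the order, so the second outcome is possible but not certain.

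**Step 3: size.** Inputs:

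- 28 patients enrolled and to be reported (section 1.3.2);
- planned cohorts of 3 to 6 subjects (section 2.1);
- analysis on the FAS, meaning anyone given any fraction of a dose (sections 2.2 and 3.4.2);
- number of Grade 5 TEAEs: not given.

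In a group of *n* subjects, let *a* be those with at least one Grade 3 or 4 TEAE and *b* those with a Grade 5 TEAE but no Grade 3 or 4 TEAE. The Grade 3-or-higher rate is (*a* + *b*)/*n*. With the filter applied first, the table as specified gives *a*/*n*. The difference is *b*/*n*. The same holds when both are restricted to drug-related events. For *b* = 1:

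- all patients, assuming all 28 were dosed: 1/28 = 3.6 percentage points;
- cohort of 6: 1/6 = 16.7 points;
- cohort of 3: 1/3 = 33.3 points.

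A replaced subject (section 1.4.4) who received drug stays in the FAS, so a cohort can exceed 6. For an assumed cohort of 8, the shift is 1/8 = 12.5 points.

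For *b* = 0 the subject-level shift is zero. With the filter first, a subject who also has another Grade 3 or 4 TEAE is still counted at subject level, and only the affected preferred-term or organ-class rows change.

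**The case against.** The strongest reply is that nothing here is stated wrongly. Text and title agree, and a table labelled Grades 3 and 4 that counts Grades 3 and 4 is correct as labelled. It understates only a different quantity, Grade 3-5, which the SAP never promised. That is true, and the shifts above should be read as differences from a Grade 3-or-higher rate, not as errors in the Grade 3/4 rate.

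Fatal events are also covered elsewhere. The by-severity table has no ceiling. A related fatal TEAE falls within the by-relationship and serious-related tables, and the listings carry grade, relationship and outcome. Section 1.4.1 builds the cohort number into each subject identifier, so a tally by cohort for 28 patients is short work. If the by-severity table shows no Grade 5, the related count is zero as well. All this stands, with one reservation: the by-severity table helps only if severity there means CTCAE grade, and section 3.4.2 names severity and grade as separate items.

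The overall TEAE summary is known by title only and might include such a row. The SAP does not say so, and an unspecified row is not a planned one. The loss through the counting rule is conditional, as shown above.

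Finally, the study was terminated, no hypothesis tests are planned, and no decision rule in the SAP uses this table. This lowers the stakes. It does not supply the missing count, and it makes the descriptive safety tables a larger share of what is reported.

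**Conclusion.** The concern holds. As specified, the severe and drug-related severe TEAE summaries exclude Grade 5, and no other by-cohort table is specified to give the drug-related Grade 5 or Grade 3-5 count. The gap is in tabulation, since the subject-level data are listed in full.

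Its size depends on events the SAP does not report. It is zero with no Grade 5 TEAE. For one subject with a Grade 5 TEAE and no Grade 3 or 4 TEAE, it is 3.6 points overall and 16.7 to 33.3 points in a cohort of planned size, or less in a cohort enlarged by replacements.

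This rests on three assumptions: CTCAE 4.03 has Grade 5 as its top grade, which the SAP does not state but is common knowledge; all 28 enrolled patients were dosed; and the Grade 3/4 filter is applied as written. It is a cheap improvement that should be made. It does not invalidate the report.

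**What to change.** In section 3.4.2, replace the Grade 3 or Grade 4 restriction in both places, all TEAEs and drug-related TEAEs, with *Grade 3 or higher (Grades 3, 4 and 5)*. Change the table title in section 4.1.3.2 to match, and show Grade 5 as its own row or column for each dose cohort.

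With no upper limit, the order in which the filter and the highest-grade rule are applied no longer removes anyone: a subject whose worst grade for a term is 5 stays in the row.

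The cost is a wording change and a changed filter in summaries that are already planned. No new data are needed. Reported severe-TEAE rates may come out less favourable if Grade 5 events occurred, more visibly so in a small cohort.
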